However, in iRECIST it is clearly recommended to carefully consider the continuation of immunotherapy at the first stage of iUPD. This decision should be thoroughly discussed with both subject and referring physicians and made only in case of subjective stable tumor disease or clinically suspected pseudoprogression. New lesions in a potentially curative therapy approach could be biopsied in order to enable a more reliable differentiation of rare pseudoprogression from more frequent PD and to be able to initiate an early modification of the tumor therapy before the subject may no longer tolerate it due to a physical deterioration. In the case that a biopsy is not technically feasible or only feasible with a significantly increased risk, the confirmation of the less probable delayed therapy response can be represented by a follow-up after 4 to 8 weeks in subjectively stable tumor subjects during this period.

According to RECIST v1.1, the RECIST working group did not believed that there were sufficient data available to recommend implementation of a metabolic and/or functional imaging response parameter. An exception is the use of fluorodeoxyglucose (FDG)-PET imaging as an adjunct to determination of progression if a positive FDG-PET at follow-up corresponds to a new site of disease confirmed by CT. However, the actual literature does not support the non-invasive differentiation of true progression from pseudoprogression by PET/CT.

Evaluation of Best Overall Response

For iRECIST, the BOR is the best time point response recorded from the start of immunotherapy until the end of treatment. Immune unconfirmed disease progression will not override a subsequent BOR of iSD, iPR, or iCR.

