### Statistical Analysis Plan

Regeneron Pharmaceuticals Inc. / Protocol: CMP-001-010 IQVIA Biotech (Confidential) Project # RZA44091

Immune Objective Response Rate (iORR)

iORR is defined as the proportion of subjects with an immune best overall response (iBOR) of confirmed immune complete response (iCR) or confirmed immune partial response (iPR) based on immunotherapy Response Evaluation Criteria in Solid Tumors (iRECIST) by Investigator assessment.

Subjects who continue study treatment beyond PD per RECIST v1.1 will be assessed by the Investigator according to iRECIST. Subjects with an iCR or iPR per iRECIST must have a confirmatory assessment performed at least 4 weeks after the initial assessment where response was declared by the Investigator and all scans should be performed at least 2 weeks after the previous CMP-001 IT injection to prevent injection-related pseudoprogression.

The confirmed iORR will be calculated as the number of subjects with a confirmed iCR or iPR divided by the number of subjects in the analysis population [iORR = (confirmed iCR + confirmed iPR)/number of subjects]. The two-sided 95% Clopper-Pearson CIs will be calculated for the iORR.

The immune best overall response (iBOR) will be derived as below: iCR > iPR > iSD > iCPD > iUPD > NE

If assessments are not performed or cannot be assessed following iUPD, and there is no subsequent iCPD, iSD, iPR or iCR, iUPD will be continue be used and the subject will be censored at the date of iUPD.

*Immune Duration of Response (iDOR).* 

iDOR is defined as the time from the date of the first immune response (iCR or iPR) to the date of immune confirmed progressive disease (iCPD) by Investigator assessment.

iDOR is only defined for Subjects who have a confirmed iBOR of iCR or iPR. Subjects with a response of iCR or iPR must have a repeat tumor assessment performed no less than 4 weeks after the criteria for response are first met. The first date at which an iCR or iPR response was noted will be used to calculate iDOR, not the date of the confirmatory tumor assessment. Subjects who did not have iCPD or death will be censored at the date of their last disease assessment. Censoring rules are detailed in Table 1b.

*Immune Progression-Free Survival (iPFS).* 

Regeneron Pharmaceuticals Inc. / Protocol: CMP-001-010 IQVIA Biotech (Confidential) Project # RZA44091

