iPFS is defined as the time from date of first dose of study drug to date of iCPD per iRECIST as assessed by Investigator or death, whichever occurs first. Censoring rules are detailed in Table 1b.

Table 1a: Censoring Rules for the PFS/DOR

Situation	Outcome	Date	Event Description/ Censoring Reason
PD per RECIST v1.1 on/before new anticancer therapy or data cutoff date, whichever is earlier	Event	Earliest date of tumor assessment documenting PD	PD per RECIST v1.1
Death without PD per RECIST v1.1 and not receiving new anticancer therapy on/before data cutoff date	Event	Date of death	Death without PD per RECIST v1.1
[PFS only] Subjects with no post-baseline assessments	Censored	Date of First Dose of Study Drug	No Adequate Disease Assessment per RECIST v1.1
No PD per RECIST v1.1 or Death as of data cutoff date and subject not received new anticancer therapy or received it after the data cutoff date	Censored	Date of last disease assessment on/before data cutoff date	Alive without Documented PD
No PD per RECIST v1.1 or Death as of data cutoff date and new anticancer therapy started before the data cutoff date	Censored	Date of last disease assessment prior to new anticancer therapy	Subsequent Anti-cancer Therapy without Documented PD
PD per RECIST v1.1 or Death after new anticancer therapy and the new anticancer started before data cutoff date	Censored	Date of last disease assessment prior to new anticancer therapy	Documented PD or Death after Subsequent Anti-cancer Therapy
PD per RECIST v1.1 or Death after new anticancer therapy and the new anticancer started after data cutoff date	Censored	Date of last disease assessment on/before data cutoff date	Documented PD or Death after Subsequent Anti-cancer Therapy
PD per RECIST v1.1 or Death immediately following two or more consecutive disease assessments missed since the last adequate disease assessment	Censored	Date of last adequate tumor assessment prior to missing assessments	PD or Death after Missing >= 2 Consecutive Disease Assessments
Withdrew consent or lost to follow- up before PD per RECIST v1.1 or Death	Censored	Date of last adequate disease assessment	Discontinued from Study without Documented PD or Death

Regeneron Pharmaceuticals Inc. / Protocol: CMP-001-010 IQVIA Biotech (Confidential) Project # RZA44091

Table 1b: Censoring Rules for the iPFS/iDOR

Situation	Outcome	Date	Event Description/ Censoring Reason

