iCPD per iRECIST between scheduled disease assessments on/before new anticancer therapy or data cutoff date, whichever is earlier	Event	Earliest date of tumor assessment documenting iUPD	iCPD per iRECIST
Death without iCPD per iRECIST and not receiving new anticancer therapy on/before data cutoff date	Event	Date of death	Death without iCPD per iRECIST
[iPFS only] iUPD per iRECIST at the time of PD per RECIST v1.1, continued study treatment without further tumor assessments as of data cutoff date	Censored	Date of the last tumor assessment on/before data cutoff date	No Adequate Disease Assessment per iRECIST
iUPD per iRECIST, continued study treatment with subsequent disease assessments but no confirmed PD (i.e., iCPD not assigned) or Death as of data cutoff date and subject not received new anticancer therapy or received it after the data cutoff date	Censored	Date of the last tumor assessment as of data cutoff date	Alive without Documented iCPD
iUPD per iRECIST, continued study treatment, but started a new anti-cancer therapy before data cutoff date without evidence of iCPD or Death	Censored	Date of the last tumor assessment prior to new anti-cancer therapy	Subsequent Anti-cancer Therapy without Documented iCPD
iCPD per iRECIST or Death after new anticancer therapy and the new anticancer started before data cutoff date	Censored	Date of last disease assessment prior to new anticancer therapy	iCPD or Death after Subsequent Anti-cancer Therapy
iCPD per iRECIST or Death after new anticancer therapy and the new anticancer started after data cutoff date	Censored	Date of last disease assessment on/before data cutoff date	iCPD or Death after Subsequent Anti-cancer Therapy
iUPD per iRECIST, continued study treatment, iCPD or Death immediately following two or more consecutive disease assessments since the last adequate disease assessment	Censored	Date of last adequate tumor assessment prior to the first missed assessment	iCPD or Death after Missing >= 2 Consecutive Disease Assessments
Withdrew consent or lost to follow-up before iCPD per iRECIST or death	Censored	Date of last adequate disease assessment	Discontinued from Study without Documented iCPD or Death

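### SAP Table 1b row 1 dates immune progression to the earliest iUPD with no reset after recovery and covers only unscheduled confirmations, in conflict with the iDOR and iPFS definitions, which end at iCPD.

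*SAP*

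**What the plan says.** SAP VIII.A starts iDOR at the first iCR or iPR and ends it at iCPD by Investigator assessment. For the other endpoint, "iPFS is defined as the time from date of first dose of study drug to date of iCPD per iRECIST as assessed by Investigator"; a death that comes earlier is also an event. Both definitions refer to Table 1b for censoring rules.

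Table 1b has one row that makes iCPD an event. Its situation is "iCPD per iRECIST between scheduled disease assessments on/before new anticancer therapy or data cutoff date", taking the earlier of the two, and its date is "Earliest date of tumor assessment documenting iUPD". The only other event row is death without iCPD. Every other row naming an iCPD outcome is a censoring row. The matching row of Table 1a, for RECIST progression, has no scheduling limit.

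Both documents expect recovery after iUPD. Protocol Appendix E states: "Immune unconfirmed disease progression will not override a subsequent BOR of iSD, iPR, or iCR". The SAP's iBOR order is "iCR > iPR > iSD > iCPD > iUPD > NE", so a subject with iUPD and then a confirmed iPR or iCR is an immune responder and enters the iDOR set.

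On who is assessed, SAP VIII.A says: "Subjects who continue study treatment beyond PD per RECIST v1.1 will be assessed by the Investigator according to iRECIST". Table 1b row 3 speaks of "iUPD per iRECIST at the time of PD per RECIST v1.1". Protocol 7.2 reads differently: it has the Investigator apply iRECIST to all disease assessments.

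**The concern.** Text and table give two different event dates for the same endpoint. The table's date also has no reset. If a first iUPD resolves and a different, later iUPD is the one confirmed, a literal derivation still goes back to the first. For iDOR that can place the event before the response, a negative time that the Kaplan-Meier analysis in SAP VIII.C cannot use. For iPFS it discards months in which the subject had recovered.

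The scheduling limit adds a second inconsistency. Two subjects with the same clinical course are dated by different rules depending only on whether the confirming scan was a scheduled one. iDOR and iPFS are listed secondary endpoints, with medians and event-free rates planned.

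**Working it through.** **Inputs.** Scans are at W13D1 and every 9 weeks after, with a -7 day window (Protocol Table 1, footnote u). Progression is confirmed at least 4 weeks after the initial PD; Protocol 7.2.4.1 sets no upper limit. SAP VIII.A gives months as (event date - start date + 1)/30.4375 for DOR and PFS. It prints no formula for iDOR or iPFS; I assume the same one, since VIII.C says the same methods apply. The SAP states no figure of its own for this rule, so there is none to reproduce. The visit sequences are illustrative.

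**Study days**, (week - 1) × 7 + 1: W13 = 85, W17 = 113, W22 = 148, W31 = 211, W35 = 239, W40 = 274, W44 = 302, W49 = 337.

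**Sequence 1.** iUPD W13, iPR W22 (later confirmed), new iUPD W40, iCPD on an unscheduled scan at W44.

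| Event dated to | iDOR (months) | iPFS (months) |
|---|---|---|
| Earliest iUPD (row 1, literal) | (85 - 148 + 1)/30.4375 = -2.04 | 85/30.4375 = 2.79 |
| iUPD that was confirmed | (274 - 148 + 1)/30.4375 = 4.17 | 274/30.4375 = 9.00 |
| iCPD (text) | (302 - 148 + 1)/30.4375 = 5.09 | 302/30.4375 = 9.92 |

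**Sequence 2, stable disease only.** iUPD W13, iSD W22, new iUPD W31, iCPD on an unscheduled scan at W35. iPFS is 2.79 by literal row 1, 211/30.4375 = 6.93 by the confirmed iUPD, and 239/30.4375 = 7.85 by iCPD.

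**Sequence 3, response first.** iPR W13 (confirmed), iUPD W22, iSD W31, new iUPD W40, iCPD W44. Literal row 1 gives iDOR (148 - 85 + 1)/30.4375 = 2.10, against 6.24 by the confirmed iUPD and 7.16 by iCPD. The value is shortened but not negative.

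**Scheduled confirmation.** Take sequence 1 with iCPD found at the scheduled W49D1 visit (days 330 to 337). Row 1 does not apply. The text dates the event at iCPD, giving iDOR 183/30.4375 = 6.0 to 190/30.4375 = 6.2 and iPFS 10.8 to 11.1. The mismatch does not need a recovery. With a single iUPD at W13, an iCPD on an added scan at day 113 is dated to day 85 (iPFS 2.8). An iCPD at scheduled W22D1 is dated by the text to day 148 (148/30.4375 = 4.9).

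**How many subjects.** Protocol 1.2.1 reports 27/98 responders including post-progression responses and 23/98 by RECIST v1.1. The difference, 4/98, is taken as the post-progression response rate (assumption; that study used pembrolizumab). For 44 subjects, 44 × 4/98 = 1.80. Assume an exponential DOR with the prior median of 19.9 months. The fraction progressing by time t is then 1 - 0.5^(t/19.9), which is 0.342 at 12 months and 0.567 at 24. Expected subjects: 1.80 × 0.342 = 0.61 to 1.80 × 0.567 = 1.02. At the lower confidence limit for the median, 6 months, the fractions are 0.750 and 0.938, giving 1.35 to 1.68.

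These figures treat every later progression as an iCPD on an unscheduled scan, so under these inputs they are upper figures. If half were confirmed off schedule (assumption), they halve to about 0.3 to 0.5, or 0.7 to 0.8 at the 6-month median.

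**The case against.** The best reply is that a sensible programmer would not derive a negative duration. iDOR is defined as running from response to iCPD, so an event before the response lies outside the definition. Row 1 describes its event as iCPD, which points naturally to the iUPD that the iCPD confirmed, and its date wording follows the pattern of Table 1a. That is a fair guess at the intent, but the SAP does not say it. The text also supports a third date, iCPD itself. The clause in SAP I.B giving the SAP precedence over the protocol does not settle a conflict inside the SAP.

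Four stronger readings are tempting and are not supported:

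- A reader might infer that an iCPD at a scheduled visit has no event or date at all. The text makes any iCPD the endpoint and dates it. What is missing is a table row that agrees with the text.
- A reader might infer that every post-progression responder gets a negative iDOR. That needs an iUPD before the first response, a later iCPD on an unscheduled scan, and a literal reading of row 1. If iRECIST is applied from the first scan, as Protocol 7.2 suggests, some responses will precede any iUPD.
- A reader might infer that backdating is itself the error. Appendix E backdates a new unclear lesion to the scan that first showed it once a repeat examination confirms it. This is not a general rule for every kind of iUPD, but it shows that backdating is not foreign to the plan.
- A reader might infer that an affected subject is close to certain. Counting all later progressions ignores the row's own limit to unscheduled scans. Protocol 7.8 also ends post-treatment scans at progression, so some progressions may never be confirmed as iCPD.

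**Conclusion.** The conflict is real, and row 1 needs rewording; this is a minor point. Row 1 and the definitions give different event dates, the row has no reset, and its scheduling limit has no counterpart in Table 1a. Taken literally, it yields an impossible iDOR when the first iUPD precedes the response, and a shortened iPFS whenever iSD, iPR or iCR intervenes before an unscheduled iCPD.

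The practical effect is small: probably no more than about one of 44 subjects with an event before the response, and fewer if only unscheduled confirmations count. This rests on the prior study's 4/98 and its 19.9-month median; the 6-month lower limit would raise the upper figure to about 1.7. The documents give no rate for iUPD followed only by iSD, or for how often iCPD is confirmed at a scheduled visit. Those subjects are not in the count; their values are shifted but remain possible ones. All analyses are labelled exploratory, iDOR and iPFS are investigator-assessed, and BICR ORR, PFS and DOR do not use Table 1b.

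**What to change.** Delete the phrase in row 1 that limits it to iCPD between scheduled assessments, and use one event date in row 1 and in both definitions in SAP VIII.A. Either of two dates removes the impossible values:

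- **Confirmed iUPD:** the first iUPD after the most recent iSD, iPR or iCR (or the first iUPD if there was none) that is subsequently confirmed as iCPD. This keeps the table's backdating and means changing the two definitions. It shortens iDOR and iPFS relative to the text by the iUPD-to-iCPD interval, 28/30.4375 = 0.9 months in sequence 1.
- **iCPD:** the date of confirmation. This keeps the definitions and changes only the table. It lengthens iDOR and iPFS relative to the table as written.

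The documents do not decide between them; the sponsor should choose one and state it. Both edits belong together, because removing the scheduling limit alone would extend the missing reset to scheduled visits. The cost is one table row, up to two sentences and the matching derivation. No new data are needed and no censoring row changes.

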## **Table 1c: Censoring Rules for the OS**

Situation	Outcome	Date	Event Description/ Censoring Reason
Death on/before data cutoff date	Event	Date of death	Death

Template No.: NVA\_TP\_CR694 Revision 3 Reference: SOPCR008, WPCR013

CONFIDENTIAL

Template Effective Date:25Aug2020 Page 27 of 43

Regeneron Pharmaceuticals Inc. / Protocol: CMP-001-010 IQVIA Biotech (Confidential) Project # RZA44091

Alive with study completed before data cutoff date	Censored	Study completion date	Alive on or before study completion date
Alive or death after data cutoff date with study continuing on/till after data cutoff date	Censored	Data cutoff date	Alive on or before data cutoff date
Lost to follow-up prior to data cutoff date	Censored	Last known alive date	Discontinued from study
Discontinued study without death and not lost to follow-up on/prior to data cutoff date	Censored	Date of study discontinuation	Discontinued from study

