- a. EOT assessments to be performed within 7 days following subject discontinuation from study treatment. Removal of a subject from CMP-001 treatment is defined as the time at which the Investigator decides to discontinue study treatment. If a subject has CMP-001 withheld for more than 3 consecutive doses for any reason during the Q3W dosing period, resumption of treatment must be discussed with the Medical Monitor, otherwise, the subject will be discontinued from study treatment and will have all EOT assessments performed.
- b. The 100DFU is a safety follow-up visit that may be conducted at the study site or via phone. This visit should occur 100 days (+7) after the EOT. NOTE: If a subject's 100DFU, PTFU, and LTSFU visits overlap, then the visits can be combined into 1 study site visit.
- c. Posttreatment follow-up will be conducted Q3mo (± 2 weeks) for all subjects who discontinue study treatment for reasons other than disease progression (either per RECIST v1.1, iRECIST, or clinical PD per Investigator) but have not met criteria for study discontinuation. These subjects should remain on study and receive disease assessments Q3mo, until discontinuation.
- d. LTSFU will be conducted Q3mo (\pm 4 weeks) after the EOT visit or the last disease assessment date in PTFU and may occur via phone.
- e. CMP-001 dosing will begin on W1D1. Weekly dosing: A window of ± 2 days is permitted for CMP-001 dosing from W1D1 to W7D1. The first dose of CMP-001 may be administered SC or IT, at the discretion of the Investigator; all subsequent doses are planned to be administered IT until no injectable lesions remain. Subjects must complete all 7 weekly CMP-001 doses before moving to the Q3W dosing schedule. Q3W dosing (W10D1+): A window of ±3 days is permitted for CMP-001 dosing from W10D1 throughout the study. When nivolumab is permanently discontinued due to an immune related AE, CMP-001 must also be permanently discontinued. Refer to Section 5.3 for Treatment Compliance.
- f. Nivolumab dosing will begin on W1D1 and continue Q3W throughout the study. When CMP-001 injection and nivolumab dosing fall on the same day, CMP-001 injection will be given before nivolumab dosing. Refer to Section 5.1.1 for Nivolumab Dosing.

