- s. To be eligible, subjects must have progressive disease according to RECIST v1.1 within 12 weeks of the last dose of a PD-1 blocking antibody (either monotherapy or combination therapy). Disease progression on PD-1 blocking antibody must be confirmed by PI assessment using baseline imaging or imaging at the time of response and 2 consecutive scans 4 weeks apart demonstrating sustained progression. The confirmatory scan may serve as the Baseline for this study if completed within 30 days before the start of study treatment. Radiographic and/or photographic imaging must be submitted for BICR eligibility verification. If available, historic photographic imaging collected at screening may be used to verify subject eligibility. Subjects must have a minimum of one target lesion not intended for IT injections identified at baseline.
- t. Baseline CNS imaging by contrast-enhanced CT or MRI must be provided at Screening; on-study CNS imaging is required in presence of clinical symptoms or if CNS disease was present at Baseline.
- u. Disease assessments will be performed predose beginning at W13D1 (-7 days) and repeated every 9 weeks (-7 days) (eg, W22D1, W31D1, etc.). A response (complete response, partial response, immune complete response, or immune partial response [per RECIST v1.1 or immunotherapy Response Evaluation Criteria in Solid Tumors]) will be confirmed with follow-up disease assessments performed at least 4 weeks after the date of initial response. Disease assessments will continue every 9 weeks after the confirmatory scans. All scans should be performed at least 2 weeks after the most recent CMP-001 IT injection to account for injection-related pseudoprogression. Disease assessments may be performed every 12 weeks for subjects with a response continuing more than 1 year. Refer to Section 7.2. for Disease Assessments. If a CR is observed in a subject, sites should continue to obtain confirmation photographs at subsequent assessments.

TABLE OF CONTENTS

	ATOR'S AGREEMENT	
SPONSOR	PROTOCOL APPROVAL	3
PROCEDU	JRES IN CASE OF EMERGENCY	4
SYNOPSIS	35	
LIST OF T	ABLES	24
LIST OF F	IGURES	24
LIST OF A	BBREVIATIONS AND DEFINITIONS OF TERMS	25
1.	INTRODUCTION	28
1.1.	Background	28
1.2.	CMP-001	29
1.2.1.	Previous Clinical Studies With CMP-001	29
1.3.	Nivolumab	30
1.3.1.	Nivolumab Mechanism of Action	30
1.3.2.	Nivolumab Clinical Activity	30
1.3.3.	Benefit/Risk Assessment	30
1.4.	Study Rationale	31

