7.9. Long-Term Survival Follow-up

Subjects who discontinue study treatment and PTFU will be contacted by the site according to the Schedule of Assessments (Table 1) for LTSFU, which will continue until death, withdrawal of consent, lost to follow-up, or End of Clinical Trial.

In this study, OS is a key endpoint of the study. Post-study follow-up is of critical importance and is essential to preserving participant safety and the integrity of the study. Participants who discontinue study treatment must continue to be followed for collection of outcome and/or survival follow-up data as required until death or the conclusion of the study.

The Sponsor may request that survival data be collected on all treated participants outside of the protocol defined window (Schedule of Assessments, Table 1). At the time of this request, each participant will be contacted to determine their survival status unless the participant has withdrawn consent for all contacts or is lost to follow-up.

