9.5.6. Overall Survival

Overall survival will be calculated as the time from first dose of study treatment to the date of death due to any cause. Subjects who are alive at the time of analyses will be censored at the time of last study contact. Median OS will be calculated using the Kaplan-Meier method.

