### G. Ad-hoc Analysis

There will be an ad-hoc analysis planned with the trigger event being two disease assessments after the enrollment of the last subject. The ad-hoc analysis of the endpoints will follow the efficacy analysis methods described in Section VIII below as well as the safety analysis methods detailed in Section IX below for the exploratory Phase 2 study.

The following subject information, efficacy-related and safety related data displays will be produced for the purpose of the ad-hoc analysis. Unless stated

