## Statistical Analysis Plan

Regeneron Pharmaceuticals Inc. / Protocol: CMP-001-010 IQVIA Biotech (Confidential) Project # RZA44091

subsequent therapy will be used. Details of the censoring rules are provided in Table 1a.

DOR will be calculated as follows:

DOR (months) = (Event/Censoring Date – Response Start Date + 1) / 30.4375

Progression-Free Survival (PFS)

Progression-free survival is defined as the time from first dose of study treatment to the date of documented PD based on RECIST v1.1 by BICR or death from any cause, whichever occurs first. Subjects who are alive and progression-free at the time of analyses will be censored in the analyses at the date of their last disease assessment. For subjects who started a subsequent anti-cancer therapy before having a documented PD, the overall response assessment evaluated after new anti-cancer treatment will not be considered for PFS calculation, and the last disease assessment prior to the start of the subsequent therapy will be used. Details of the censoring rules are provided in Table 1a.

PFS will be calculated as follows:

PFS (months) = (Event or Censoring Date – First Dose Date + 1) / 30.4375

All events of RECIST v1.1 disease progression or death will be counted regardless of whether the event occurred while the subject was on study drug or had previously discontinued treatment. Subjects who do not experience disease progression or death before the analysis cutoff date will be censored at the date of last adequate tumor assessment. Date of censoring for these subjects will be based on the last tumor assessment prior to missing the assessments. Censoring rules are summarized in Table 1a. If a subject meets the criteria for more than 1 censoring rule, PFS will be censored at the earliest censoring date.

Secondary Efficacy Assessments by Investigator

The secondary efficacy endpoints of ORR, BOR, DCR, DOR and PFS by investigator assessments will be derived using the same approach as above.

Overall Survival (OS)

Overall survival will be calculated as the time from first dose of study treatment to the date of death due to any cause. Subjects who are alive or lost to follow-up at the time of the analysis data cutoff will be censored at the time of last known alive date, or at data cutoff date, whichever occurs first. Censoring rules are detailed in Table 1c, and the last contact date will be derived as shown in Table 2.

OS will be calculated as follows:

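### SAP Table 1c censors ongoing subjects for OS at the data cutoff, against the SAP's own text; Table 1a's no-assessment row for PFS does not exclude deaths

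*SAP*

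**What the plan says.** **Overall survival.** The OS paragraph of SAP VIII.A states that subjects alive or lost to follow-up at the analysis cutoff "will be censored at the time of last known alive date, or at data cutoff date, whichever occurs first", and refers to Table 1c for the detailed rules and to Table 2 for deriving the date of last contact. Table 1c has a row for "Alive or death after data cutoff date with study continuing on/till after data cutoff date", whose censoring date is the data cutoff itself. Only its lost-to-follow-up row uses the last known alive date. Protocol 9.5.6 says: "Subjects who are alive at the time of analyses will be censored at the time of last study contact".

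**Contact schedule.** Protocol Table 1, footnote d: "LTSFU will be conducted Q3mo", with a window of 4 weeks either side. A survival sweep is optional under Protocol 7.9: "The Sponsor may request that survival data be collected on all treated participants outside of the protocol defined window".

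**Planned look with ongoing subjects.** SAP VI.G: "There will be an ad-hoc analysis planned with the trigger event being two disease assessments after the enrollment of the last subject". OS and PFS are both among its displays.

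**Progression-free survival.** In SAP Table 1a, the row "PFS only] Subjects with no post-baseline assessments" is censored at first dose. The row above it makes death without progression, and without new anticancer therapy, an event at the date of death. The first on-study scan is at Week 13 (Protocol Table 1, footnote u: "Disease assessments will be performed predose beginning at W13D1").

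**The concern.** The SAP gives two censoring dates for the same ongoing subject, and the clause in SAP I.B that lets the SAP override the protocol cannot settle a conflict inside the SAP. Censoring at the cutoff treats the time since last contact as time observed alive. If a death in that interval has not yet reached the database, the subject stays in the risk set without the death being counted, and the Kaplan-Meier curve is too high.

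The PFS point is separate. A subject who dies before the Week 13 scan without new therapy satisfies both the no-assessment row (censored at first dose) and the death row (event). The SAP's tie-break applies only when several censoring rules compete, so it does not choose between an event and a censoring. The SAP expects such subjects: VIII.A assigns a best response of PD to progression deaths before any post-baseline assessment.

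Two programmers working from the same SAP could therefore produce different OS and PFS estimates.

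**Working it through.** No figure in the plan is at stake. The check compares the rules and then sizes the difference.

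**1. OS rules for an ongoing subject last contacted before the cutoff**

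| Source | Censoring date |
|---|---|
| SAP VIII.A text | last known alive date |
| SAP Table 1c | data cutoff date |
| Protocol 9.5.6 | last study contact |

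The text and the protocol agree; the table is the outlier.

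**2. How long the gap can be.** A contact made on schedule and a next one made at the end of its window are 3 + 28/30.4375 = 3.92 months apart.

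**3. When it matters.** The ad-hoc trigger is two scans (W13, W22) after the last enrolment. W22D1 falls 21 weeks after W1D1: 147/30.4375 = 4.8 months (simulated as 4.9). Many subjects would then be ongoing.

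**4. Size of the OS effect.** Kaplan-Meier simulation with n = 44 (SAP II.C) and 1,500 to 3,000 replicates per scenario (800 to 1,200 for the same-extract runs in step 5). Assumed, not in the documents: exponential survival with median 12 months; 14-month accrual; 70% of subjects in 3-monthly phone follow-up (gap since last contact uniform on 0 to 3 months); the rest at 3-weekly treatment visits (0 to 0.7 months). The table gives 12-month OS at the ad-hoc cutoff.

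| Scenario | Table 1c | Last known alive | Full information | Table 1c excess (points) |
|---|---|---|---|---|
| Base case, deaths since last contact unknown | 52.4% | 49.4% | 49.7% | 2.7 |
| Median 18, 50% by phone | 64.7% | – | 62.8% | 1.9 |
| Median 9, 90% by phone | 43.1% | – | 39.3% | 3.8 |
| Accrual 10 months | 54.6% | – | 49.7% | 4.9 |
| Accrual 18 months | 51.9% | – | 49.9% | 2.0 |
| All deaths known, alive contacts not updated | 49.7% | 47.0% | 49.7% | 0 |

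Repeat runs of the base case gave 52.6% to 52.7% under Table 1c, against 49.9% with full information. About 11 of the 44 subjects are at risk at 12 months, and the replicate SD is about 9 points. With the cutoff 12 months after last enrolment, the excess falls to 0.2 to 0.4 points.

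A simpler simulation (6 to 18 months from first dose to cutoff, every subject's gap uniform up to 3 or 3.9 months) gave the same picture. With median 12, Table 1c gives 53.6% to 55.0% against a true 50.0%. With median 24, it gives 73.3% to 74.4% against 70.7%.

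**5. Deaths and alive contacts from the same extract, taken some months after the cutoff**

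| Extract delay (months) | 0 | 1 | 2 | 4 |
|---|---|---|---|---|
| Table 1c | 53.1% | 51.7% | 50.4% | 49.8% |
| Earlier of last known alive and cutoff | 49.7% | 50.2% | 49.8% | 49.6% |

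Full information here is 49.8% to 50.1%. The text rule is close to it at every delay; Table 1c becomes so only as the delay grows.

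**6. PFS.** Suppose k of 44 subjects die unscanned, before any other event or censoring. Counted as events, they multiply all later PFS rates by (44 − k)/44; censored at first dose, they do not. The ratio of the two results is 44/(44 − k), with k assumed:

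- k = 1: 44/43 = 1.023
- k = 2: 44/42 = 1.048
- k = 4: 44/40 = 1.100

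**The case against.** **The Table 1c row may cover only subjects whose status is known at or after the cutoff.** Its mention of later deaths suggests this, and for such subjects both rules give the cutoff. But ongoing subjects last seen before the cutoff would then have no row, so the table would still need correcting.

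**The direction of bias is not fixed.** This stands. The documents do not say how deaths are ascertained. If every death to the cutoff is learned while alive contacts are not refreshed, Table 1c is right (49.7%) and last-known-alive censoring is too low (47.0%). The remedy must therefore include an ascertainment rule as well as the new date.

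**The effect is small and descriptive.** This also stands. All analyses are exploratory, no OS test is planned, and a survival sweep is already permitted and would make the rules agree.

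**The PFS text largely settles the death.** True: VIII.A counts death from any cause and censors subjects who are alive and progression-free. The Table 1a defect is a missing qualifier, and probably an oversight, since the next two rows do exclude progression and death.

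**A never-scanned subject who dies after missing both W13 and W22 also meets the missed-assessments row.** Correct. That overlap is a further point, which the Table 1a change below does not settle.

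**Conclusion.** Both points hold. Table 1c contradicts the text it is meant to detail, and Table 1a's no-assessment row overlaps its death row without a stated order.

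The OS consequence is an overstatement of about 2 to 5 points in 12-month survival at the ad-hoc analysis, provided that deaths since last contact are unknown at extraction and the assumed survival, accrual and contact patterns are roughly right. It is a few tenths of a point with a year's further follow-up, and nil at the final analysis, when no subject is still continuing.

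The PFS consequence is smaller in practice because the text points to the right answer. Its size depends on the number of unscanned deaths, which the documents do not give. Both endpoints are secondary and the primary ORR is untouched. The tables should be corrected, but the study's main conclusion does not depend on it.

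**What to change.** - **Table 1c:** for subjects continuing on study, set the censoring date to the earlier of the Table 2 last known alive date and the data cutoff.
- **Ascertainment:** add one sentence requiring deaths and alive contacts to come from the same extract. Alternatively, run the Protocol 7.9 survival sweep at the cutoff, in which case the two rules agree.
- **Table 1a:** restrict the no-assessment row to subjects with no death on or before the cutoff that qualifies under the death-event row, and state that a qualifying death takes precedence over that row.

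The cost is two table cells and one sentence in the SAP. No new data are needed unless the sweep is chosen.
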